**Figure 1: Study Visit Schedule**

**Imiquimod treatment** - Subjects randomized to the VGX-3100 with imiquimod arm will apply imiquimod 5% cream to the vulvar lesion(s) beginning in the evening on Day 0, and will continue to apply imiquimod cream three times per week for 20 weeks (inclusive of administration in the evening of VGX-3100 dosing). Subjects unable to tolerate imiquimod treatment may reduce their dosing frequency, and will document their use on the imiquimod dosing log provided.

[figure not shown]
**Efficacy Assessment:** Biopsies obtained as part of the study at Screening will be from the region of most advanced disease as judged by the Investigator, and must be approximately 4 mm in length. Visible lesion must remain after screening biopsy to ensure measurement on study.

Visualization of a normal appearing vulva by vulvoscopy is insufficient evidence to confirm disease regression. Disease regression will be based on histopathologic assessment at Week 48, 74, and 96. Subjects will be monitored during the course of the study by vulvoscopy. Lesion(s), defined as areas that stain acetowhite, will be assessed during vulvoscopy at Screening, Day 0 and Weeks 4, 12, 27, 48, 74 and 96. Using standardized high resolution digital photographic imaging, vulvar lesion(s) will also be quantitatively measured at Screening, Day 0, and Weeks 4, 12, 27, 48, 74 and 96.

The decision process following results of the Week 48 biopsy are described in [Figure 2](#) below and as follows: At Week 48, the subject will undergo repeat vulvar punch biopsy/biopsies of the same lesion as study start, but from the region of potentially most advanced disease based upon the judgment of the Investigator (see [Table 2](#) for Minimally Required Biopsy Procedures). If after evaluation of biopsy tissue by the PAC there is no evidence of HSIL (Subgroups A or B), the subject will continue to Week 74 for vulvoscopy, and biopsy of the same lesion as study start.

[figure not shown]
If after evaluation of the biopsy tissue HSIL remains, but there is a reduction in the qualifying lesion(s) size or no change in lesion size from baseline (Subgroups C or D), the Investigator has the option to give the subject a 5th dose of VGX-3100 at Week 52, and the subject will continue on study with vulvoscopy and biopsy at Week 74. Alternatively, the Investigator may choose to treat the subject with surgical or standard treatment, and the subject will continue on study without further biopsy. A qualifying lesion is defined as a vulvar lesion which is confirmed to be HPV-16 and/or HPV-18 positive and have histologically confirmed vulvar HSIL by the PAC at screening.

**Figure 2: Decision process at Week 52**

[figure not shown]
The decision process following results of the Week 74 biopsy are described in [Figure 3](#) and as follows: At Week 74, the subject will undergo repeat vulvar punch biopsy/biopsies of the same lesion as study start from the region of potentially most advanced disease based upon the judgment of the Investigator (see [Table 2](#)). If after evaluation of biopsy tissue by the PAC there is no evidence of HSIL (Subgroups A or B), the subject will continue to Week 96 for vulvoscopy, and biopsy of the same area from the region of potentially most advanced disease based upon the judgment of the Investigator. If HSIL remains but there is a reduction in lesion size or no change in lesion size from baseline (Subgroups C or D), the Investigator has the option to give the subject a 6th dose of VGX-3100 at Week 78, and the subject will continue on study with vulvoscopy and biopsy at Week 96. Alternatively, the Investigator may choose to treat the subject with surgical or standard treatment, and the subject will continue on study without further biopsy.

**Figure 3: Decision Process at Week 78**

The decision process following results of the Week 74 biopsy are as described in Figure 4 and as follows: At Week 96, the subject will undergo repeat vulvar punch biopsy/biopsies of the same lesion as study start from the region of potentially most advanced disease based upon the judgment of the Investigator (see Table 2). If there is no vulvar HSIL (Subgroups A or B), no further procedures are required. If after evaluation of biopsy tissue by the PAC there is vulvar HSIL (Subgroups C or D), or worsening disease (Subgroup E), the subject will receive surgical or other standard treatment.

**Figure 4: Evaluation process at Week 100**

In the event of worsening disease at any time (i.e., Subgroup E – any increase in lesion area from baseline or worsening to cancer), the subject will receive surgical treatment per the Investigator's judgment and will continue on study through Week 100 with vulvoscopy, but without further study treatment or biopsy. If at any time in the study carcinoma is discovered, subjects will receive surgical treatment, and be discontinued from study treatment. The event will be reported as an SAE per section 7.1.4. If wide excision is required, the sample obtained will be sent to the PAC for evaluation.

Definition of Responder and Non-responder: Responder and non-responder definitions (Table 3) take into account both histopathologic regression of vulvar HSIL and virologic (HPV-16/18) clearance from tissue samples since HPV persistence is an important factor in the clinical progression of HSIL. A treatment responder is defined as a subject with no histologic evidence of vulvar HSIL and no evidence of HPV-16 or HPV-18 in vulvar tissue at evaluation and who did not receive any non-study related treatment for vulvar HSIL. A treatment non-responder is a subject with histologic evidence of vulvar HSIL or vulvar carcinoma at evaluation, or a subject with evidence of HPV-16/18 at evaluation, or a subject who received non-study related treatment for vulvar HSIL. Any case of histologically confirmed progression from HSIL to carcinoma is considered a non-responder.

Safety Assessment: Subjects will be monitored for:

- 1) Local and systemic events for 7 days following each VGX-3100 dose as noted in the Participant Diary
- 2) All adverse events including SAEs, SUSARs, UADEs, and other unexpected AEs for the duration of the study.

All subjects will be followed for 100 weeks.

Data Safety & Monitoring Board (DSMB): The DSMB will meet quarterly to review safety data and tissue regression and viral clearance results. The DSMB will be charged with advising the Sponsor if there appears to be a safety issue. No formal interim analysis is planned. The following stopping rules will be applied:

- If at any time during the study one-third (1/3) or more of the subjects experience an Adverse Event of Special Interest (AESI), further enrollment and study treatment will be halted immediately until a thorough investigation has been conducted by the Medical Monitor, Principal Investigator (PI) for the trial, and the DSMB.
- If any SAE (or potentially life-threatening AE) or death assessed as related to study treatment occurs, further enrollment and study treatment will be halted immediately until a thorough investigation has been conducted by the Medical Monitor, PI for the trial, IRB (if applicable) and the DSMB.
- If three or more subjects in this study experience the same Grade 3 or 4 adverse event, assessed as related to study treatment, further enrollment and study treatment will be halted immediately until a thorough investigation has been conducted by the Medical Monitor, PI for the trial, and the DSMB.
- In the event of two identical, unexpected, Grade 4 toxicities, assessed as related to study treatment, further enrollment and study treatment will be halted immediately until a thorough investigation has been conducted by the Medical Monitor, PI for the trial, IRB (if applicable) and the DSMB.

The sponsor or designee will notify all Investigators and IRBs/EC (if required) regarding the outcome of any investigation stemming from a Study Pause.

Immunogenicity Assessment: The study will explore humoral and cell mediated immune responses to VGX-3100, and VGX-3100 with imiquimod, in blood samples taken at baseline (i.e., Screening and Day 0 prior to dosing) and Weeks 15, 27, 48, 74 and 96. Vulvar samples will also be analyzed for evidence of immune responses at Screening and Weeks 48, 74 and 96.

Virologic Assessment: Tissue samples will be obtained to characterize vulvar HPV infection at Screening, Weeks 48, 74 and 96. Cervical samples, oropharyngeal rinse, vulvar, vaginal, and intra-anal tissue swab samples will be obtained to characterize HPV infection at the following time points: Day 0 prior to dosing (OP, cervical, vulvar, vaginal and intra-anal), Week 4 (Vulvar only), Week 12 (Cervical and vulvar) and Weeks 27, 48, 74 and 96 (OP, vulvar, vaginal and intra-anal). At Weeks 48 and 96, cervical sample will also be collected.

HLA haplotyping: A sample from one time point during the study will be tested to explore the relationship between subject HLA haplotypes and regression.

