The decision process following results of the Week 74 biopsy are described in [Figure 3](#) and are as follows: At Week 74, the subject will undergo repeat vulvar punch biopsy/biopsies of the same lesion as at study start Investigator(see [Table 2](#)). If after evaluation of biopsy tissue by the PAC there is no evidence of HSIL (Subgroups A or B), the subject will continue to Week 96 for vulvoscopy and biopsy of the same lesion as at study start. InvestigatorIf HSIL remains but there is a reduction in lesion size or no increase in lesion size from baseline (Subgroups C or D), the Investigator has the option to give the subject a 6th dose of VGX-3100 at Week 78, and the subject will continue on

study with vulvoscopy and biopsy at Week 96. Alternatively, the Investigator may choose to treat the subject with surgical or standard treatment, and the subject will continue on study without further biopsy.

The decision process following results of the Week 74 biopsy are as described in [Figure 4](#) and are as follows: At Week 96, the subject will undergo repeat vulvar punch biopsy/biopsies of the same lesion as study start, but from the region of potentially most advanced disease based upon the judgment of the Investigator. (see [Table 2](#)). If there is no vulvar HSIL (Subgroups A or B), no further procedures are required. If after evaluation of biopsy tissue by the PAC there is vulvar HSIL (Subgroups C or D), or worsening disease (Subgroup E), the subject will receive surgical or other standard treatment.

In the event of worsening disease (i.e., Subgroup E - any increase in lesion area from baseline or worsening to cancer), the subject will receive surgical treatment per the Investigator's judgment and will continue on study through Week 100 with vulvoscopy, but without further study treatment or biopsy. For a finding of carcinoma, subjects will receive surgical treatment, and be discontinued from study treatment. The event will be reported as an SAE per [section 7.1.4](#). If wide excision is required, the sample obtained will be sent to the PAC for evaluation.

Pre-biopsy Vulvoscopy Finding	Minimally required procedure
No acetowhite lesion	Vulvar punch biopsy and lesion photography; biopsy should be conducted of the same qualifying lesion as study entry from the region of potentially most advanced disease based upon judgment of the Investigator.

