All eligible subjects who consent to participate in the study will receive four to six doses of 6 mg of VGX-3100 administered by IM injection followed by EP. The first dose will be administered as soon as possible following confirmation of the HSIL diagnosis, HPV-16/18 status and all other eligibility criteria, but no more than 10 weeks following collection of the subject's biopsy specimen used for diagnosis by the PAC.

Each dose of VGX-3100 will be administered in a 1 mL volume IM followed immediately by EP with the CELLECTRA™ 2000 device. As shown in [Figure 1](#), study subjects will receive at least 4 doses of VGX-3100 and potentially a 5th and 6th dose depending upon their disposition with regard to histologic and lesion area changes. The first dose will be administered on Day 0, the second at Week 4, the third at Week 12, and the fourth dose will be administered at Week 24. Subjects with no HSIL at Week 48 (Subgroups A and B) will receive 4 doses. Subjects with HSIL at Week 48, who have a reduction in lesion size or no increase in lesion size from baseline (Subgroups C or D), may receive a fifth dose of VGX-3100 administered IM with EP at Week 52 per the judgment of the Investigator. Subjects with HSIL at Week 74, who have a reduction in lesion size or no increase in lesion size from baseline (Subgroups C or D), may receive a sixth dose of VGX-3100 administered IM with EP at Week 78 per the judgment of the Investigator. Subjects in Subgroup E may receive surgical treatment per the judgment of the Investigator. All subjects are scheduled to be followed to Week 100.

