**Study Population:**

Inclusion:

1. Must understand, agree and be able to comply with the requirements of the protocol. Subjects must be willing and able to provide voluntary consent to participate and sign a Consent Form prior to study-related activities;
2. Women aged 18 and above
3. Vulvar infection with HPV types 16 and/or 18 confirmed by screening biopsy;
4. Vulvar tissue specimen/blocks must be collected within 10 weeks prior to anticipated date of first dose of study drug and have histologically confirmed vulvar HSIL by the Pathology Adjudication Committee at screening;
5. Must be judged by the Investigator to be an appropriate candidate for the protocol-specified procedure (i.e. excision or biopsy) required at Week 48;
6. Must have vulvar HSIL that is accessible for sampling by biopsy instrument and of adequate size to ensure that a visible lesion remains after an approximately 4 mm screening biopsy;
7. Must have vulvar HSIL that can be completely demarcated for area measurement;
8. Must meet one of the following criteria with respect to their reproductive capacity:
  - a) Is post-menopausal as defined by spontaneous amenorrhea for more than 12 months or spontaneous amenorrhea for 6-12 months with FSH level >40 mIU/mL;
  - b) Is surgically sterile due to absence of ovaries or due to a bilateral tubal ligation/occlusion performed more than 3 months prior to screening;
  - c) Women of Child Bearing Potential (WOCBP) are willing to use a contraceptive method with failure rate of less than 1% per year when used consistently and correctly from screening until 6 months following the last dose of investigational product. Acceptable methods are the following:
    - i) Hormonal contraception: either combined or progestin-alone including oral contraceptives, injectable, implants, vaginal ring, or percutaneous patches. Hormonal contraceptives must not be used in subjects with a history of hypercoagulability (e.g., deep vein thrombosis, pulmonary embolism);
    - ii) Abstinence from penile-vaginal intercourse when this is the subject's preferred and usual lifestyle;
    - iii) Intrauterine device or intrauterine system;
    - iv) Male partner sterilization at least 6 months prior to the female subject's entry into the study, and this male is the sole partner for that subject.
9. Has normal screening electrocardiogram (ECG) or screening ECG with no clinically significant findings as judged by the Investigator.

Exclusion:

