- c Screening 12-lead ECG, complete blood count (CBC), serum electrolytes, blood urea nitrogen (BUN), creatinine (Cr), glucose, ALT, CPK and urinalysis performed within 45 days prior to first dose administration.
- d Negative spot urine pregnancy test is required at screening and prior to each study treatment, vulvoscopy and biopsy/surgical excision.
- e At least 34 mL (4 x 8.5 mL yellow (ACD) tubes) whole blood and 4 mL serum per time point. At least 68 mL whole blood and 8 mL serum should be collected prior to first dose. One additional 8.5 mL yellow (ACD) tube to be collected at Day 0, Week 15 and 48 for microRNA analysis.
- f At least 51 mL [6 x 8.5 mL yellow (ACD) tubes] whole blood and 4 mL serum should be collected at Week 27.
- g HLA testing will be performed once from an existing PBMC sample.
- h HPV genotyping and Pap smears are performed on the same ThinPrep® cervical specimen.
- i An additional visit may be scheduled to perform vulvoscopy if worsening of disease is suspected. Biopsies should not be performed at any visit other than at entry (Screening), Week 48, and Weeks 74 and 96 for Subgroups C and D unless the Investigator suspects invasive cancer. All biopsy samples and/or excision samples must be sent to the PAC for review.
- j Photography of the acetowhite stained qualifying lesion(s) must be performed prior to and after biopsy, and at all vulvoscopy examinations. If a pre-biopsy digital photograph is not available for a historical biopsy sample at screening, a post biopsy photo will be sufficient. Additionally, standardized high resolution digital photographic imaging should be obtained during examinations of the vagina if lesions are identified, for documentation.
- k Tissue specimen from all excised tissue must be reviewed by the PAC and residual vulvar tissue from entry, Week 48, 74 or Week 96 specimen(s) (paraffin blocks or unstained slides) must be sent to the central pathology laboratory for HPV testing.
- l HPV genotyping is performed on vulvar tissue specimen using a PCR based assay.
- m Potential dosing at Week 52 and Week 78 is applicable for partial responders only.
- n Subjects will take home imiquimod plus an imiquimod dosing log to document their use of imiquimod. Administration of imiquimod begins on Day 0.

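### Stopping biopsy after lesion growth at any time conflicts with the Week 48 biopsy required of every woman, and can drop a few untreated likely non-responders from the primary analysis

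*Protocol*

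**What the plan says.** **The stop on biopsy.** The version 2.1 synopsis, in the text under Figure 4, opens with "In the event of worsening disease at any time". It defines worsening (Subgroup E) as any rise in lesion area over baseline, or cancer. Such a woman has surgery if the Investigator so judges and "will continue on study through Week 100 with vulvoscopy, but without further study treatment or biopsy". The Study Design text of the synopsis also makes surgery optional: "Subjects in Subgroup E may receive surgical treatment per the judgment of the Investigator".

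**When growth can be seen.** The Efficacy Assessment text of the synopsis says "vulvar lesion(s) will also be quantitatively measured at Screening, Day 0, and Weeks 4, 12, 27, 48, 74 and 96". Three of these visits fall after baseline and before Week 48.

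**The Week 48 biopsy.** The same text says "At Week 48, the subject will undergo repeat vulvar punch biopsy/biopsies of the same lesion as study start". Inclusion criterion 5 requires each woman to be an "appropriate candidate for the protocol-specified procedure (i.e. excision or biopsy) required at Week 48". The Biopsy row of Table 1 marks Week 48 for everyone. Footnote i restricts by subgroup only the two later visits: "Week 48, and Weeks 74 and 96 for Subgroups C and D unless the Investigator suspects invasive cancer".

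**How the endpoint is classed.** The non-responder definition (synopsis; Table 3 in version 2.0) needs an adverse tissue finding or treatment for vulvar HSIL outside the study regimen. Lesion growth alone is not on the list. Section 8.4 (version 2.0) admits to mITT only dosed women who have the endpoint, and Section 8.11.6 (version 2.0) rules out imputation. The version 2.1 summary of changes lists no change to either section.

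**The concern.** Two instructions in one version of the protocol give opposite answers about whether tissue for the primary endpoint is taken from a woman whose lesion has grown by Week 4, 12 or 27. If a site follows the stop and does not operate, her primary endpoint is missing because her disease got worse.

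That is an outcome-dependent loss. Women with growing lesions are likely non-responders, so removing them from the denominator pushes the reported response rate upward. At stake are the response estimate and its confidence interval, which are the main product of a small phase 2 study that calls itself a pilot.

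**Working it through.** **Inputs.** Allocation 24 and 12 (Section 3). Assumed response 20% and 28%, null 2%, one-sided 0.025 per arm, 80% power, 90% evaluable (Section 8.3, version 2.0). Exact Clopper-Pearson analysis, with success requiring p < 0.025 and a lower bound above 0.02 (Section 8.9, version 2.0). The number of unoperated, unbiopsied women with growth is not given, so it is assumed below.

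**1. The plan's own figure.** The smallest n with at least 80% exact power is 21 at 20% (success at 3 or more responders, power 0.821) and 10 at 28% (success at 2 or more, power 0.817). Dividing by 0.90 gives 23.3 and 11.1, rounded up to 24 and 12, total 36. This matches.

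**2. One woman followed through the text.** Her lesion grows at Week 12 and the Investigator does not operate.
- Under the Figure 4 text she has no more biopsies, so no Week 48 tissue. Under the Week 48 text, Table 1 and footnote i she is biopsied at Week 48.
- If the first instruction is followed, there is no tissue finding. Unless she is treated, no non-responder clause applies.
- Section 8.9 opens the efficacy window 14 days before the visit week and gives no closing date, so later tissue could still count. The Week 96 step sends women with worsening disease to surgery or standard treatment, and the treatment clause has no time limit.
- She is therefore lost to mITT only if she is never operated on, otherwise treated or biopsied.

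**3. Size of the bias.** With x responders among n women, of whom k non-responders are dropped, the observed rate is x/(n − k) = (x/n) × n/(n − k). Assume k = 1 or 2 per arm, starting from all dosed women:

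| Arm | n/(n − 1) | n/(n − 2) | Assumed rate would read |
|---|---|---|---|
| VGX-3100 alone, n = 24 | 24/23 = 1.04 | 24/22 = 1.09 | 20% → 20.9% to 21.8% |
| With imiquimod, n = 12 | 12/11 = 1.09 | 12/10 = 1.20 | 28% → 30.5% to 33.6% |

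Whole-number examples with exact 95% intervals:
- 5/24 = 20.8% (7.1 to 42.2) becomes 5/22 = 22.7% (7.8 to 45.4).
- 3/12 = 25.0% (5.5 to 57.2) becomes 3/10 = 30.0% (6.7 to 65.3).

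More generally, if a share q is dropped, the rate is divided by 1 − q. A true 20% reads 22.2%, 25.0% or 28.6% at q = 10%, 20% or 30%. Nothing in the protocol suggests the larger shares; they only show the range.

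**4. Effect on the test.** The smallest x with P(X ≥ x | p = 0.02) < 0.025 is 3 for n = 13 to 24 (0.0118 at n = 24, 0.0093 at n = 22) and 2 for n = 2 to 12 (0.0231 at n = 12). The lower-bound rule gives the same counts. Going from 24 to 22 or from 12 to 10 changes neither threshold. Even at q = 30% of 22 women, the chance of success moves only from 0.0093 to 0.0126 under the null and from 0.846 to 0.864 at a true 20%.

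**The case against.** The best reply is that the literal reading is not the intended one.
- In the synopsis text on the Week 48 and Week 74 decisions, women treated surgically or with standard care go on without biopsy, so there the stop follows treatment. The Figure 4 sentence likewise mentions surgery first.
- Section 3.2 (version 2.0) words the rule without the any-time phrase ("In the event of worsening disease (i.e., Subgroup E - any increase in lesion area from baseline") and places it after the Week 48 to 96 steps.
- Read literally, the rule would also end dosing for any growth at Week 4, against the minimum of four doses in the Study Design text.
- Section 6 (version 2.0) makes the schedule binding. Table 7 (version 2.0) lets a woman with HSIL on an unscheduled biopsy keep to scheduled visits.

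Most of this stands as evidence of intent, and it makes the affected group small. It does not remove the conflict. The Figure 4 sentence attaches the stop to worsening rather than to having been operated on, and no text shown says that it gives way. Section 6 demands adherence to the design requirements generally, and the stop is one of them.

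A reader might infer more than the documents support:
- *That every woman with lesion growth drops out.* Operated women are non-responders under Table 3, which the summary of changes says was widened to cover surgery.
- *That the endpoint is irretrievably lost at Week 48.* The open-ended window in Section 8.9 and the Week 96 treatment step can still bring a woman back into mITT.

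**Conclusion.** The conflict is real, and its consequence follows from the written rules, but only for a narrow group: women with growth before Week 48 who are handled under the literal stop and then have no surgery, other treatment or tissue through Week 100. Their number is unknown and probably small, and some may already sit within the 10% non-evaluable allowance (2.4 of 24 and 1.2 of 12).

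The harm is a modest upward bias in the estimate and its interval: a factor of 1.04 to 1.09 in the larger arm and 1.09 to 1.20 in the smaller, if one or two non-responders are lost per arm. It would be wrong to infer a threat to the superiority conclusion, because the success thresholds do not change.

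This rests on Sections 8.4, 8.9 and 8.11.6 as they stand in version 2.0. The version 2.1 text of Sections 3.2 and 8 is not in the part at hand, and Figures 2 to 4 are not shown. A separate SAP might class such women as non-responders, but it could not settle whether the biopsy is taken.

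**What to change.** In the synopsis text under Figure 4 and in Section 3.2, state that the stop on biopsy applies only after surgery or a finding of carcinoma, and that a woman with lesion growth who has not been operated on still has the scheduled Week 48 biopsy.

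In Section 8.4 or 8.9, add: *A dosed subject with lesion growth (Subgroup E) who has no evaluable Week 48 tissue is included in mITT as a non-responder.* The sentence must reach the untreated woman without tissue, since treated women are already classed.

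The cost is one clarifying sentence in two places and one analysis sentence. No visit or procedure is added, because the Week 48 biopsy is already scheduled. The growth criterion and the Investigator's freedom to operate stay as they are. The downside is that the observed response rate may be slightly lower.
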